6.0 TREATMENT PLAN

[figure not shown]

Fig. 1 PATCH Trial Schema. Dz: Disease A: Arm

Sub-Study 1: 100 patients 2 interim analyses

Arm 1: High dose HCQ: Hydroxychloroquine 400 mg twice a day for up to 14 days

Arm 2: Placebo: 2 pills twice a day for up to 14 days cross over for progressive disease

Sub-Study 3: 200 participants 2 interim analyses

Arm 1: High dose HCQ: Hydroxychloroquine 600 mg daily for 2 months

Arm 2: Placebo: 3 pills once a day for 2 months crossover to HCQ 600 mg daily if PCR positive

7.0 DETAILS OF STUDY TREATMENT

7.1 Hydroxychloroquine

Mechanism of Action: The mechanism of action is not fully understood. Previously it was thought that HCQ and other chloroquine derivatives are weak bases that deacidify lysosomes through purely chemical basis. Recently our group has identified the missing molecular target of HCQ as palmitoyl protein thioesterase 1 (PPT1).

Storage and formulation: HCQ tablets are manufactured by Sandoz. Each tablet contains 200 mg hydroxychloroquine sulfate (equivalent to 155 mg base). It is dispensed in a tight, light-resistant container as defined in the USP/NF. HCQ should be stored at room temperature up to 30° C (86° F).

Pharmacokinetics: The PK of HCQ is characterized by a large volume of distribution, binding to red blood cells, and long time to peak concentration and steady state. Population PK studies in cancer patients have demonstrated dose proportional change in exposure.

Administration: Hydroxychloroquine is an oral medication, requiring participants in sub-studies 1 and 3 on study to keep an electronic study diary. Diary must be submitted at 14 days (sub-study 1) and 2 months (sub-study 3). Hydroxychloroquine will be provided by IDS. Tablets of HCQ are available in 200 mg strength. When HCQ is administered in divided doses (every 12 hours) two daily doses of HCQ should be taken 12 hours apart, for example, 9 am and 9 pm, and documented clearly on the patient drug diary. The HCQ schedule may be adjusted if necessary to minimize gastrointestinal side effects.

For complete information please refer to the package inserts at <http://dailymed.nlm.nih.gov/dailymed/>

7.2 Placebo: Excipient only manufactured to match hydroxychloroquine. Manufactured at Temple University.

7.3 Concomitant Medication, Drug-Drug interactions and Procedures

Participants in sub-study 3 must be instructed not to take any medications, except tylenol, including over the counter products such as NSAIDs, without first consulting with the investigator. Participants in sub-study 1 must be instructed not to take any medications, including Tylenol and over the counter products such as NSAIDs, without first consulting with the investigator.

Drug Interactions

The following medicines are allowed but should be carefully monitored.

Digoxin: Concomitant HCQ and digoxin therapy may result in increased serum digoxin levels.

Insulin or antidiabetic drugs: As HCQ may mildly enhance the effects of a hypoglycemic treatment, a decrease in doses of insulin or antidiabetic drugs may be required.

Drugs that prolong QT interval and other arrhythmogenic drugs: HCQ can prolong the QT interval and should not be administered with other drugs that have the potential to induce cardiac arrhythmias. Also, there may be an increased risk of inducing ventricular arrhythmias if HCQ is used concomitantly with other arrhythmogenic drugs. A full list of these drugs can be found at <https://crediblemed.org>

Antiepileptics: The activity of antiepileptic drugs might be impaired if co-administered with HCQ.

The PATCH Trial

Cyclosporin: An increased plasma cyclosporin level was reported when cyclosporin and HCQ were co-administered.

Because HCQ has known effects on P450 enzymes, patients requiring anti-convulsants may be treated with any of the non-enzyme inducing anti-convulsants which include: felbamate, valproic acid, gabapentin, lamotrigine, tiagabine, topiramate, or levetiracetam. Due to the fact that both zonisamide and HCQ accumulate in red blood cells, zonisamide should be avoided if possible. All other concomitant medications are permitted.

The following medications are not allowed during the study. The sponsor must be notified if the subject receives any of these during the study:

1. Sub-study 1: Any investigational or off-label antiviral therapy
2. Immunosuppressive medications, including, corticosteroids at doses exceeding 10mg/day of prednisone or equivalent, methotrexate, azathioprine, and TNF-alpha blockers. Use of immunosuppressive medication for the management of study treatment-related AEs or in subjects with contrast allergies is acceptable. In addition, use of topical, inhaled and intranasal corticosteroids is permitted
3. Live attenuated vaccines during the study
4. Herbal and natural remedies must be avoided

7.4 Duration of Protocol Treatment and Follow-up.

Sub-Study 1 duration of treatment is up to 2 weeks or at the time of release from quarantine. HCQ will be stopped in all patients at the time of release from quarantine

Sub-Study 3 duration of treatment is 2 months with assay to assess SARS CoV2 every 2 weeks.

7.5 Crossover from Control to HCQ arm. For Sub-Study 1 all participants are un-blinded upon symptom progression (see response assessment below) after at least 7 days of treatment or upon hospitalization if this occurs prior to 7 days of treatment. If the participant was assigned to placebo, he/she has the option to crossover to receive HCQ 400 mg po bid for up to 2 weeks or until criteria for release from quarantine are met (See 1.0 primary endpoint). During these 2 weeks of HCQ treatment, the patient will continue to complete the daily diary. An appropriately delegated study team member will call the patient daily to assess worsening symptoms and AEs. Patients who are not improving will be sent to the hospital for further care. Participants who have progressive symptoms and are subsequently hospitalized as related to COVID-19 will not be crossed over to receive HCQ at the time of unblinding.

In sub-study 3 participants who have worsening symptoms as defined as fever, significantly worsening cough, shortness of breath or hypoxia but do not require hospitalization and tests positive for SARS-CoV2 virus are allowed to cross over to receive HCQ, or treated with an alternative therapy per physician's choice. Once the positive test returns, the CRC will email IDS to initiate unblinding IDS will inform the CRC and clinical investigator if the patient was on placebo. The clinical investigator will contact the subject and inform them that if they were on placebo they would have the option of being treated with HCQ 600 mg qd. If the patient agrees, the clinical investigator will place the order in EPIC for HCQ 600 mg qd through IDS. Drug will be delivered to the patient's home. During these 2 weeks of HCQ 600 mg po qd treatment, clinical investigators will call the patient every 1-3 days depending on the severity of symptoms to assess worsening symptoms and AEs. Patients who are not improving will be sent to the hospital for further care.

8.0 TOXICITY CRITERIA, MONITORING, DOSE DELAYS AND MODIFICATIONS

8.1 Toxicity Criteria

This study will utilize the Common terminology criteria for adverse events version 5.0 (CTCAE v 5.0).

https://ctep.cancer.gov/protocolDevelopment/electronic_applications/docs/CTCAE_v5_Quick_Reference_8.5x11.pdf All appropriate treatment areas should have access to a copy of the CTCAE v 5.0 grading tables.

Property of University of Pennsylvania
Confidential

8.2 Dose Delays

Major Events are grade 3 and 4 hematologic and non-hematologic toxicities that are not treatment -related. Treatment should be delayed for major events if HCQ may further complicate the non-treatment related event. If a major event requires a delay of treatment, treatment must be delayed until toxicity is resolved (\leq Grade 2 or \leq Baseline). For treatment-related toxicities and major events, if toxicity is not resolved in \leq 14 days, patient will be taken off treatment unless there is an exception granted by the medical monitor.

8.3 Ocular toxicity. The only toxicity that requires discontinuation of HCQ is retinopathy. Published literature indicates HCQ retinopathy is idiosyncratic and is uncommon in patients receiving HCQ for less than a few years. Our ongoing study of dabrafenib, trametinib, and HCQ (BAMM; NCTNCT02257424) found no clinically meaningful ocular toxicity in 10 patients studied extensively with serial ocular exams (25). Although HCQ retinotoxicity can occur at shorter than expected intervals with the use of high dose (>5 mg/Kg/day of real body weight) treatment protocols, the cumulative doses required to elicit a retinopathy were only reached after about a year of treatment (26). Thus, we do not anticipate cumulative doses in this trial will reach retinotoxic levels (>200 grams) and have, therefore, not included mandatory ocular exams in this protocol. However, participant will be advised to report with any visual changes at which point a comprehensive ophthalmic exam will take place to decide whether HCQ should be permanently discontinued. As a precaution, patients with renal failure will also be excluded from the trial.

Laboratory monitoring is not recommended for HCQ use in rheumatoid arthritis. The American College of Rheumatology guidelines for the treatment of rheumatoid arthritis recommends no laboratory testing for outpatients that are started on hydroxychloroquine (27). HCQ doses for rheumatoid arthritis range from 400mg daily to 400mg twice a day encompassing the dosing paradigms in Sub-study 1 and sub-study3.

8.3 Safety of HCQ in pregnancy obviates the need for pregnancy monitoring. Numerous case series and a recent large scale epidemiological study demonstrate the safety of HCQ in outpatient pregnant women with systemic lupus erythematosus (28). Therefore we are not requiring pregnancy test prior to starting HCQ in sub-studies 1 and 3. Potential participants that are known to be pregnant are excluded.

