Oral fluid collection: Participants will be asked to collect oral fluid using the RNAPro-Sal collection kit manufactured by Oasis Diagnostics (<https://4saliva.com/products/rnapro-sal/>). These kits will be provided to the participant with the drug supply. The participant will have clear instructions on how to collect oral fluid on themselves. This process consists of inserting the gauze tip in the mouth for 4 minutes, removing and pushing the syringe to squeeze the fluid into the container. A video will be sent to the participant's email address and texted to them providing visual instructions on use. Participants should produce an early morning saliva sample from the posterior oropharynx (ie, coughed up by clearing the throat) before tooth brushing and breakfast, because nasopharyngeal secretions move posteriorly and bronchopulmonary secretions move by ciliary activity to the posterior oropharyngeal area while the patients are in a supine position during sleep. Participants will be instructed to collect oral fluid at the following time-points in the containers provided (before taking the first dose of study and every 2 weeks after that). The collected oral fluid should be placed in the freezer in a sealed container. This container will be collected after the participant is at the end of their participation. The participant will then wipe the container surface with disinfectant and return to site. If the participant becomes quarantined or hospitalized with COVID-19, a primary contact for the participant will be contacted and if asymptomatic and/or COVID-19 negative the driver will pick up the saliva using the same procedure.

8.5 Hydroxychloroquine Dose Reduction.

In outpatient arms 1 and 3, any AE of \geq Grade 2 or adjusted QTc prolongation to >500ms and attributed as possibly, probably or definitely related solely to HCQ will result in dose holiday and/or dose reduction of HCQ as described in Table 5. No more than 1 dose reductions are allowed.

Table 3: Hydroxychloroquine Dose Reduction Schema

Sub-Study	Dose mg/day	First dose reduction
1	400 mg twice daily	400mg daily
3	600 mg daily	400 mg daily

- If the second dose reduction is not tolerated, then the patient should discontinue the treatment.

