10.3 Off treatment/Off Study

Each participant has the right to withdraw from the study at any time without prejudice. The investigator may discontinue any person's participation for any reason, including adverse event or failure to comply with the protocol. Should a participant withdraw from the study, the reason(s) must be stated on the case report form, and a final evaluation of the participant should be performed. Reasons for withdrawal include the following:

Progression of Disease: Remove participant from protocol therapy at the time progressive disease is documented. Progression of disease is left to the discretion of the treating physician/ sub-Investigator; however, the following guidelines are provided to help decision making for discontinuing study drug:

Sub-study 1: Progression of disease can be confirmed if there is increase in COVID-19 symptom score for 2 days in a row and is three points higher than baseline. Once criteria for release from quarantine is met in SS1 the patient is off study. Once the person is hospitalized for COVID-19 in sub-study 1 the subject is off study. Participants who have progressive symptoms and are subsequently hospitalized as related to COVID-19 will not be crossed over to receive HCQ at the time of unblinding.

Sub-study 3: Development of new symptomology consistent with COVID-19: e.g. fever, cough, shortness of breath and SARS-COV2 test positivity would lead to unblinding. If on placebo the subject can crossover to HCQ for treatment and stay on study for 14 days or release from quarantine. If the subject was on HCQ the subject is off study and will be instructed to seek medical attention through their primary care physician

Extraordinary Medical Circumstance: If at any time the treating physician feels constraints of this protocol are detrimental to the participant's health remove the participant from protocol therapy.

Participant's refusal to continue treatment: In this event, document the reason(s) for withdrawal.

Failure to comply with protocol (as judged by the investigator such as compliance below 80%, failure to maintain appointments, etc.).

Withdrawal from treatment per patient choice: Patients may withdraw from study treatment at any point in the study for any reason. These subjects are allowed to withdraw from treatment but continue to participate with any of the other study procedures for the intended 2 month period.

Delay in treatment > 7 days due to toxicity

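### Protocol Sections 8.2, 8.3, 8.5 and 10.3 disagree on when toxicity ends study drug, and the trigger in 8.5 cannot be reached as written

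*Protocol*

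**What the plan says.** Four sections of the current protocol deal with ending study drug because of toxicity.

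- Section 8.3 (Ocular toxicity): "The only toxicity that requires discontinuation of HCQ is retinopathy". The sentence has no qualifier.
- Section 8.2 (Dose Delays), immediately before it: "For treatment-related toxicities and major events, if toxicity is not resolved in" at most "14 days, patient will be taken off treatment unless there is an exception granted by the medical monitor". Its scope is treatment-related toxicities and major events of any organ. Major events are defined there as grade 3 and 4 toxicities not related to treatment.
- Section 8.5 (Hydroxychloroquine Dose Reduction), below Table 3: "If the second dose reduction is not tolerated, then the patient should discontinue the treatment". The paragraph above the table says: "No more than 1 dose reductions are allowed". Table 3 has one reduction column.
- Section 10.3 (Off treatment/Off Study) includes among its reasons for withdrawal: "Delay in treatment > 7 days due to toxicity".

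None of the rules in 8.2, 8.5 (as quoted) or 10.3 is confined to the eye. No section ranks them or refers to the others on this point.

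**The concern.** Two study physicians facing the same persistent non-ocular toxicity can each follow the protocol and reach different answers on whether, and when, the participant comes off drug. Sub-Study 3 enrolls health care workers without recent symptoms, or with a negative test for them, and treats them for two months. Its stopping rules therefore should not depend on which section is consulted.

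There is also a data consequence. The adverse event reporting period (Protocol Section 11.0, repeated in the SAP) closes at the last administration of study treatment. The date on which drug is stopped therefore helps set the window for treatment-related adverse events, the Sub-Study 3 secondary objective. Exposure and the count of toxicity discontinuations depend on the same decision.

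Section 10.3 says that participants who leave treatment by choice may continue other study procedures, but it does not say this for the toxicity delay. If a toxicity stop becomes a study withdrawal, the outcome may be missing, and the SAP does not impute missing values.

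**Working it through.** The plan gives no figure to reproduce. The check sets the passages side by side and applies them to one case.

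**Inputs.** Section 8.2: unresolved at 14 days. Section 10.3: delay over 7 days. Section 8.5: one reduction allowed, stop after the second. Section 7.4: Sub-Study 1 treatment up to 2 weeks, Sub-Study 3 treatment 2 months. The SAP (Study Design) gives eight weeks, so 8 × 7 = 56 days.

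**Case.** A non-ocular, treatment-related toxicity of grade 3 or higher, so that Section 8.5 holds the drug and Section 8.2 counts it as unresolved. The hold is assumed to start on the day the toxicity starts. This aligns two clocks that differ: 8.2 counts time to resolution, 10.3 counts the treatment delay.

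| Day of hold | Section 10.3 | Section 8.2 | Section 8.3 |
|---|---|---|---|
| 1 to 7 | not triggered | not triggered | stop not required |
| 8 to 14 | listed reason for withdrawal | not triggered | stop not required |
| 15 onward | listed reason for withdrawal | off treatment unless an exception is granted | stop not required |

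From day 8 to day 14, Section 10.3 stands against Sections 8.2 and 8.3. From day 15, Sections 8.2 and 10.3 stand against 8.3.

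**Where each limit can operate.** If the hold starts on treatment day s, hold day 8 is treatment day s + 7 and hold day 15 is treatment day s + 14.

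- Sub-Study 3 (56 days): the 7-day limit can operate if s + 7 ≤ 56, that is s ≤ 49. The 14-day limit can operate if s + 14 ≤ 56, that is s ≤ 42. Both are live for most of the treatment period.
- Sub-Study 1 (14 days): the 7-day limit can operate if s + 7 ≤ 14, that is s ≤ 7. The 14-day limit needs s + 14 ≤ 14, that is s ≤ 0. It can hardly take effect before planned treatment ends.

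**Section 8.5.** Reductions allowed: 1. Reduction whose failure triggers stopping: the second. Since 2 > 1, the trigger cannot occur. The original protocol in the same supplement allowed two reductions and its Table 3 had a second column, which probably explains the leftover sentence. As the text now stands, Section 8.5 does not say what follows if the single permitted reduction is not tolerated.

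**The case against.** The strongest reply is context. The sentence in 8.3 opens a paragraph on ocular toxicity whose purpose is to explain why eye examinations are not mandatory. A natural reading is that retinopathy alone ends treatment on occurrence, while other toxicities go through hold, reduction and then conditional stopping. That may well be what the authors meant, but the text does not say so.

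Several parts of the reply do stand and limit the point:

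- A reader might infer that 8.3 tells staff to keep dosing. It does not. Saying that a stop is not required neither forbids stopping nor orders continuation, and Section 8.5 holds drug for grade 3 or higher until it falls to grade 2 or lower. For such a toxicity the dispute is about formal discontinuation.
- A reader might infer that three sections flatly mandate stopping and one denies it. Section 8.2 allows a medical-monitor exception, 10.3 is a list of reasons for withdrawal, and the 8.5 trigger cannot fire. Only 8.2 is an operable mandatory rule, and it is qualified.
- A reader might see a further contradiction in the QTc criterion. Under 8.5, a QTc above 500 ms leads to a dose holiday or reduction, not to discontinuation, so it does not itself conflict with 8.3.
- A reader might size the problem from the grade 3-4 rate below 10% in Section 2.3. That rate comes from cancer patients on combination regimens, and the section itself expects most of those events not to occur in healthy people. It also counts all such events, not those that persist. It gives no estimate here.
- A reader might assume that the affected toxicities fall mainly on the HCQ arm. The documents do not establish this, and major events under 8.2 are by definition unrelated to treatment and can occur in either arm.

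**Conclusion.** The contradiction is real and lies in the current text. For a persistent non-ocular toxicity, 10.3 points to withdrawal after 7 days, 8.2 to coming off treatment after 14 days absent an exception, and 8.3 to no required stop. The sharpest operational conflict is 7 against 14 days. The remaining stopping clause, in 8.5, is unreachable. The problem bites mainly in Sub-Study 3; in Sub-Study 1 the 14-day limit has almost no room to act.

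The size is limited. No sample-size or power figure depends on these passages, and the number of participants affected cannot be estimated from the documents. The possible effects are on participant safety, on exposure, on the discontinuation count and adverse event window and, if stopping becomes study withdrawal, on missing outcomes. The day counts assume that the hold starts with the toxicity and that the toxicity is of a grade both held under 8.5 and unresolved under 8.2. The documents do not support going further and saying that one of these rules is the correct one.

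**What to change.** The sponsor should reconcile Sections 8.2, 8.3, 8.5 and 10.3 into one consistent set of toxicity-related stopping rules, state which passage governs, and have the other sections cross-reference it. The revision needs to settle:

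- how the statement in 8.3 relates to the rules in the other sections;
- the 7-day and 14-day limits, including what each clock counts from;
- the second-reduction trigger in 8.5, given that one reduction is allowed.

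It would also help to state whether a toxicity stop ends treatment only or also ends study participation. The clinical content of each rule is for the sponsor to decide; this review takes no position on it.

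The cost is small but more than a one-word edit: coordinated wording in four sections, a clinical decision by the sponsor, and a protocol amendment. Sample size and the group-sequential boundaries are untouched.

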8.4 Participant safety monitoring and data collection

8.4.1 Sub-Study 1:

Clinical symptom monitoring: Participants will be called by an appropriately delegated and credentialed member of the study team () daily at home to monitor clinical symptoms according to the following grading scales:

Table 1. Example of Daily COVID-19 Symptom tracking score table				
Symptom	Mild =1	Moderate =2	Severe =3	Score
Abdominal pain				0
Fatigue				0
Cough		2		2
Shortness of breath	1			1
Diarrhea				0
Myalgias		2		2
Headache				0
Smell disturbance				0
Other:				0
Total Score				5

The PATCH Trial

The participant will have a daily diary where this table can be filled in by the participant. The study team member will ask for each symptom and record the answers on an eCRF. At the end of the study the concordance of the participant recorded diary and the assessment made by the study team member will be determined. For discordant cases the study team member recorded AEs will be utilized for data analysis.

AE assessment: HCQ can cause nausea, constipation, diarrhea, rash. Participants will be asked if there have been changes in vision such as distortions of blurred vision. Diarrhea and nausea are known toxicities of HCQ that overlaps with the COVID-19 symptoms. In this case diarrhea or nausea can be considered COVID-19 symptoms by the study team. If an overlapping symptom is worsening while other symptoms are resolving it will be reclassified as a treatment related AE. Cardiac AEs will be assessed directly by the cardiology Sub-Investigators (see below).

Triage: An appropriately delegated and credentialed member of the study team (as example: research nurse) will document treatment-related AEs, and triage the participant for continued home quarantine versus hospitalization. Follow up with an appropriately delegated and credentialed physician investigator will be undertaken for assessment and grading of events.

Temperature Measurements: Home quarantined participants will be asked to take twice daily temperature and record the measurements on their phone. For those patients that do not have a thermometer, one will be provided by the study. The temperature records in the participant diary will be reviewed for trends within participants and in HCQ v. placebo cohorts.

Mobile Cardiac Telemetry: Participants will be provided with a mobile cardiac telemetry device (ZioAT, iRhythm Technologies). This technology will wirelessly transmit continuous monitoring to Irhythm, Inc. Irhythm will notify the study team for prolonged QTc, or life threatening arrhythmias in near real time. Dose adjustments will be performed as described below to achieve adjusted QTc <500 ms when necessary. Refusal to wear the mobile cardiac telemetry device will not prevent study participation and/or will not result in removal from the trial. Baseline QTc will be assessed by the cardiology Subl. Subsequent cardiac assessments will only be triggered by Irhythm alerts.

Oral fluid collection: Participants will be asked to collect oral fluid using the RNAPro-Sal collection kit manufactured by Oasis Diagnostics (<https://4saliva.com/products/rnapro-sal/>). These kits will be provided to the participant with the drug supply. The participant will have clear instructions on how to collect oral fluid on themselves. This process consists of inserting the gauze tip in the mouth for 4 minutes, removing and pushing the syringe to squeeze the fluid into the container. A video will be sent to the participant's email address and texted to them providing visual instructions on use. Participants should produce an early morning saliva sample from the posterior oropharynx (ie, coughed up by clearing the throat) before toothbrushing and breakfast, because nasopharyngeal secretions move posteriorly and bronchopulmonary secretions move by ciliary activity to the posterior oropharyngeal area while the patients are in a supine position during sleep. Participants will be instructed to collect oral fluid at the following time-points in the containers provided (before taking the first dose of study drug, day 3, day 7). The collected oral fluid should be placed in the freezer in a sealed container. This container will be collected after the participant is released from quarantine. The participant will then wipe the container surface with disinfectant and the ED van will come to pick up the sample. The van driver will open a bag and the participant will carefully place the container in the bag, so that the outside of the bag is not contaminated. If the participant becomes hospitalized with COVID-19, a primary contact for the participant will be contacted and if asymptomatic and/or COVID-19 negative the driver will pick up the saliva using the same procedure.

Nares swabs:

Anterior nares specimen: Participants will self-collect these samples on day 0 (start date for HCQ) before the HCQ is taken, Day 3, and day 7

The PATCH Trial

Foam swab provided: Puritan 6" Sterile Standard Foam Swab w/ Polystyrene Handle (SKU # 25-1506 1PF)

Collection instructions: Use a single foam swab for collecting specimens from both nares. Insert foam swab into 1 nostril straight back (not upwards). Once the swab is in place, rotate it in a circular motion 2 times and keep it in place for 15 seconds. Repeat this step for the second nostril using the same swab. Remove foam swab and insert the swab into the supplied tube.

Storage instructions: The collected swab should be placed into the bag marked "Nares swabs collected" and the date and time of the swab collection should be filled out Redcap. The "Collected" bag is then placed in the freezer in the same sealed container as the oral fluid.

Specimen stability for all specimen types for all tests is now as follows:

Room temperature: 5 days

Refrigerated (2 °C–8 °C): 5 days

Frozen (-20 °C): 7 days

Frozen (-70 °C): Acceptable

Specimen pickup: At the end of quarantine, or end of study procedures, the nares swabs will be collected. And shipped to Quest Diagnostics to assess viral titers. Cold packs or dry ice should be used during collection and cold packs should be used during shipping to Quest.

Pill diary: When the participant is released from quarantine the electronic pill diary must be submitted electronically.

Monitoring co-inhabitants: Appropriately delegated and credentialed study team members (as example: Clinical Research Coordinator) will ask the participant about the status of co-inhabitants daily to 14 days after the quarantine is completed to determine if the participant's co-inhabitants did or did not have symptoms or tested positive for COVID-19.

8.4.2 Sub-Study 3:

SARS-CoV-2 testing: Hospital workers will be tested for SARS-CoV-2 virus by RT-PCR every month. This will be a nasopharyngeal swab that will be processed by Quest diagnostics performed during enrollment at one month and two months. This screening NP swab will provide results in EPIC for clinical action within 72 hours. Eligibility criteria to start study medication does not require a negative PCR result to return.

Asymptomatic PCR+ at baseline: Given the 20% prevalence of asymptomatic coronavirus infection, we will need to screen 250 subjects to accrue the target enrollment of 200 to address the primary endpoint. If the PCR test returns positive while the health care worker is enrolled on the study, the participant will be notified and offered to be removed from the study or to continue with the study medication. Baseline PCR+ subjects who decide to withdraw from the study will be asked to go to occupational health and seek the care of their primary physician. Their study medication will remain blinded and the subject will be asked not to take any additional study medication. For baseline PCR+ subjects who decide to continue on study, they will be asked to keep the daily pill diary. If these subjects are asymptomatic after one week of study medication, they will be asked to return to undergo an on treatment nasopharyngeal swab. If the subject develops symptoms on study medication after 7 days of treatment, the subject will be unblinded. If the subject was assigned to placebo, they will have the option to crossover and get treatment with HCQ 600 mg qd for up to 7 days. Weekly phone calls per the sub-study 3 schedule will continue during this time. AEs will be reported as planned for the study. Baseline PCR+ subjects will be replaced in the prevention study related to the primary objective of sub-study 3 and will not count towards the target accrual or interim analysis. Baseline PCR negative subjects who screen positive at the one month or two-month mark will be considered COVID-19 positive as it relates to the primary endpoint.

Asymptomatic PCR+ at one month: These subjects will count towards the primary endpoint of sub-study 3 as an infection event. Accordingly, they will be unblinded and if on placebo they will be allowed to crossover to HCQ 600 mg qd for 2 weeks. If the subject is assigned to HCQ and turns PCR positive while asymptomatic, the subject will be stopped from study drug and referred to occupational health for standard of care management of health care worker infection. Weekly phone calls will continue. If the subject remains asymptomatic after one month, he/she will return for the one-month swab.

Clinical Symptom monitoring: Appropriately delegated and credentialed study team members (as example: CRC) will screen for symptoms 1X per week and if present will document the likely treatment related AEs. Follow up with an appropriately delegated and credentialed physician investigator will be undertaken for assessment and grading of events. Participants will be asked if there have been changes in vision such as distortions of blurred vision. Patients who develop COVID-19 symptoms will be instructed to go to occupational health for nasopharyngeal swab. The rate of conversion to PCR positive in each arm at the 2-month mark will be used to assess the primary endpoint.

Electrocardiogram Recordings: An electrocardiogram (12 lead or 6 lead) will be recorded at baseline prior to the initiation of the study drug. Those participants with an ECG in the last 6 months and no QTc prolonging medications do not need a repeat baseline ECG. One month after starting the study drug a repeat ECG will be performed to confirm excessive QTc prolongation has not occurred. If the QTc has prolonged to >500ms dose reduction as described below will be attempted to achieve a QTc of <500ms. Due to the long half-life of HCQ, study medication can be started before the baseline ECG is read.

Pill diary: Electronic pill diary will be turned in by the participant at the end of the study.

Oral fluid collection: Participants will be asked to collect oral fluid using the RNAPro-Sal collection kit manufactured by Oasis Diagnostics (<https://4saliva.com/products/rnapro-sal/>). These kits will be provided to the participant with the drug supply. The participant will have clear instructions on how to collect oral fluid on themselves. This process consists of inserting the gauze tip in the mouth for 4 minutes, removing and pushing the syringe to squeeze the fluid into the container. A video will be sent to the participant's email address and texted to them providing visual instructions on use. Participants should produce an early morning saliva sample from the posterior oropharynx (ie, coughed up by clearing the throat) before tooth brushing and breakfast, because nasopharyngeal secretions move posteriorly and bronchopulmonary secretions move by ciliary activity to the posterior oropharyngeal area while the patients are in a supine position during sleep. Participants will be instructed to collect oral fluid at the following time-points in the containers provided (before taking the first dose of study and every 2 weeks after that). The collected oral fluid should be placed in the freezer in a sealed container. This container will be collected after the participant is at the end of their participation. The participant will then wipe the container surface with disinfectant and return to site. If the participant becomes quarantined or hospitalized with COVID-19, a primary contact for the participant will be contacted and if asymptomatic and/or COVID-19 negative the driver will pick up the saliva using the same procedure.

8.5 Hydroxychloroquine Dose Reduction.

In outpatient arms 1 and 3, any AE of \geq Grade 2 or adjusted QTc prolongation to >500ms and attributed as possibly, probably or definitely related solely to HCQ will result in dose holiday and/or dose reduction of HCQ as described in Table 5. No more than 1 dose reductions are allowed.

Table 3: Hydroxychloroquine Dose Reduction Schema

Sub-Study	Dose mg/day	First dose reduction
1	400 mg twice daily	400mg daily
3	600 mg daily	400 mg daily

- If the second dose reduction is not tolerated, then the patient should discontinue the treatment.

Toxicities that may be attributable to HCQ include: nausea, anorexia, vomiting, constipation, diarrhea, rash, and visual field deficit. If any of these AEs occur at grade < 2, HCQ may be continued and the AE managed with supportive care. For any AE with a grade ≥ 3, HCQ dose will be held until the toxicity resolves to ≤ grade 2, after which HCQ may be restarted at a reduced dose as described in table 5. With particular regard to visual field deficits participants should be cautioned to report any visual symptoms, particularly difficulty seeing entire words or faces, image distortions, intolerance to glare, decreased night vision, or loss of peripheral vision. **These symptoms of retinal toxicity or subclinical evidence of retinal toxicity on eye exam should prompt drug discontinuation and ophthalmologic evaluation at Scheie Eye Institute Urgent care.** The natural course of COVID_19 is not fully understood and additional toxicities attributable to HCQ may emerge when used to treated COVID-19.

8.6 Procedure for handling of potentially contaminated material: For sub-study 1 institutional and CDC guidelines will be followed. Patients and subjects on sub-studies 1 and 3 will be instructed on safe practices for storage of oral fluid and disinfection of outer layers of bags and receptacles. Proper hand washing techniques will be reviewed with subjects. Changes in recommendations from the CDC or the University of Pennsylvania will be immediately implemented.

